Crohn's disease (CD) is a type of inflammatory bowel disease (IBD) characterized by chronic inflammation in the digestive tract. The pathogenesis of IBD involves immunological, genetic and environmental factors. Currently there is no cure for Crohn's disease and available medical and surgical treatments are expensive and often associated with significant side effects. Anti-tumor necrosis factor alpha (anti-TNF- α) agents are widely used for treatment of Crohn's disease. Electrical neuromodulation is a new treatment approach of bioelectronic medicine, involving molecular medicine, neuroscience, and bioengineering. Multiple possible mechanisms have been proposed for electrical neuromodulation in GI diseases, including central, autonomic, and/or enteric mechanisms. Vagal tone is significantly blunted in IBD and is associated with high TNF- α levels. Animal and preliminary human studies have demonstrated that electrical vagal nerve stimulation (VNS), including non-invasive vagal stimulation (nVNS), exerts an anti-inflammatory effect by harnessing the cholinergic anti-inflammatory pathway. In healthy humans nVNS has been shown to decrease tumor necrosis factor- α levels. Invasive VNS has been shown to improve inflammation in preliminary studies in patients with Crohn's disease.

Study Design: Single center open label interventional pilot study.

Estimated Enrollment: 12 participants

Aim: To assess the safety and efficacy of transcutaneous vagal stimulation in adult patients with active Crohn's disease.

Hypothesis: Non-Invasive VNS will decrease inflammation in people with Crohn's disease leading to decrease in inflammatory markers and symptoms of disease.

Outcome Measures:

Primary Outcome Measure:

1. Change in fecal calprotectin over time [16 weeks]

Secondary Outcome Measures:

1. Change in Crohn's disease activity index (CDAI) over time [16 weeks].
2. Change in serum cytokine levels over time [16 weeks]. Cytokine levels within the blood will be assessed and compared to baseline levels. The cytokines being assayed include C- reactive protein, tumor necrosis factor-alpha, Interferon-gamma, Transforming Growth Factor-beta and Interleukins (IL) - 1, 6, 10, 12, 17, 21, 23.
3. Heart Rate Variability (HRV) [Time Frame: 16 weeks]. Evaluating change in HRV from baseline until study completion.
4. Insulin levels will be collected and analyzed to see if there are any insulin changes before and after first stimulation

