Materials and Methods: Adult patients with Crohn's disease presenting to the Indiana University Medical center will be invited to participate in the study. Additionally, potential participants can receive information about participation at disease specific health fairs, and educational event.

Ages Eligible for Study: 18 to 75 Years, inclusive.

Sexes Eligible for Study: All

Inclusion Criteria:

1. Crohn's disease diagnosis for at least 3 months, confirmed by clinical, biochemical, and endoscopic evaluations.
2. Patients with CD involving the small bowel and / or colon with active symptoms with Crohn's Disease Activity Index (CDAI) > 220 despite at least one conventional therapy (corticosteroids and/or immunosuppressives) with a stable dose will be included.
3. Elevated Fecal calprotectin ≥ 200 $\mu\text{g/g}$ within the past 4 weeks prior to enrollment
4. If on corticosteroids, the dose must be stable and $\leq 20\text{mg/day}$ prednisone or equivalent for at least 14 days before entry into study.
5. If on background immunosuppressive treatment the dose must be stable with the following parameters:

6. 56 days (8 weeks) for Immunomodulators (methotrexate, 6-MP, Azathioprine) and small molecules (upadacitinib)
7. 84 days (12 weeks) for biologics (Infliximab, Adalimumab, Vedolizumab, Ustekinumab, Risankizumab)
8. Clinical laboratory evaluations (including a chemistry panel, complete blood count [CBC], and urinalysis [UA]) within the reference range for the test laboratory, unless a typical consequence of CD or deemed not clinically significant by the Investigator. Labs done clinically within the past 30 days will be used for this criterion and will not need to be repeated for inclusion in the study.
9. Colonoscopy within the previous 1 year with no evidence of colonic dysplasia or cancer.
10. Able and willing to give written informed consent and comply with the requirements of the study protocol.

Exclusion Criteria:

1. Expectation to increase corticosteroids and/or immunosuppressive treatment
2. Presence of bowel stricture with pre-stenotic dilatation
3. Presence of intra-abdominal or perirectal abscess
4. Crohn's Disease Activity Index (CDAI) < 220
5. Fistula with clinical or radiological evidence of abscess
6. Perianal CD with or without rectal involvement
7. Ileostomy, colostomy, enteral or parenteral feeding
8. Short gut syndrome.

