A handheld device (Fig. 1) (GammaCore; electroCore Inc.; Rockaway, NJ, USA), which consists of a battery powered portable stimulator with a digital control user interface that controls signal amplitude and two steel contact electrodes will deliver the nVNS electrical stimulation to the cervical Vagus nerve. The device has been approved by the U.S. Food and Drug Administration (FDA) for non-invasive Vagus nerve stimulator therapy for adjunctive use for the prevention and treatment of migraine and cluster headaches in adult patients.

The following visits will be held as part of the study

Visit 1. Screening Visit:

Subjects identified by the PI or the Sub-I, or who have been given study information at a health care event, who meet the inclusion and exclusion criteria will be consented after the study has been explained in detail to the subject and they are willing to participate in the study. They will complete the Short Inflammatory Bowel Disease Questionnaire (SIBDQ) at this time.

Patients will also be asked to complete a Crohn's Disease Activity Index (CDAI) diary for 7 days prior to the baseline visit to determine eligibility. Patient may repeat CDAI diary up to 4 times if the CDAI score does not fall in the qualifying range.

Visit 2. Baseline Visit:

1. Subjects will complete the Short Inflammatory Bowel Disease Questionnaire (SIBDQ).
2. Blood (30 ml/2 tablespoons) is collected under aseptic conditions for the inflammatory markers, cytokine levels, insulin levels, and serum samples for future analysis.
3. ECG electrodes are placed on the chest for measurement of the electrocardiogram (ECG)
4. A baseline ECG recording using the above placed electrodes will be made for 20 minutes. There is no electrical stimulation taking place currently.

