2. Stool sample for the week 8 visit can be collected and sent to the IU Health pathology lab by the subject. Request for the stool sample collection will be provided to the subject at the baseline visit. Stool for week 8 can be collected within a week of Visit 3 (Week 8 +/- 1 week)
3. Subjects will complete a CDAl diary for each week. During weeks 1-7 to be collected at Visit 3 (Week 8 +/- 1 week).

Visit 3 (8 week or 56 days +/- 5 days)

1. Subject will take one set of two stimulations during the visit to verify compliance and appropriate use of the device.
2. Subjects will complete the Short Inflammatory Bowel Disease Questionnaire (SIBDQ).
3. Blood (29 ml/2 tablespoons) is collected for the inflammatory markers, cytokine levels, and serum samples for future analysis.
4. ECG electrodes are placed on the chest for measurement of the electrocardiogram (ECG)
5. The gammacore device will be placed on the left side of the neck in line with the vagus nerve. Electrical stimulations are applied using the device for 120 seconds followed by another 120 seconds after a 60 second pause. During this time the ECG recordings will continue.
6. After the stimulation period has ended, the subject will continue to be monitored and after 20 minutes post stimulation subject will be allowed to go home.
7. The subject will be asked to continue applying one set of 2 consecutive stimuli, lasting 120 seconds each, 3 times a day till the next visit in 8 weeks.

(Week 8-week 15)

1. Subjects continue to stimulate the left vagus nerve with one set of two stimulations, 120 seconds each, 3 times a day, one in the morning after waking up, one in the afternoon after lunch and one an hour before going to bed.

2. Stool sample for the week 16 visit can be collected and sent to the IU Health pathology lab by the subject. Request for the stool sample collection will be provided to the subject at the week 8 visit. Stool for week 16 can be collected within a week of Visit 4 (Week 16 +/- 1week)
3. Subjects will complete a CDAI diary for each week. During weeks 8-15 to be collected at Visit 4 (Week 16 +/- 1week).

Visit 4 (16 week or 112 days +/- 5 days)

1. Subject will take one set of two stimulations during the visit to verify compliance and appropriate use of the device.
2. Subjects will complete the Short Inflammatory Bowel Disease Questionnaire (SIBDQ).
3. Blood (29 ml/2 tablespoons) is collected for the inflammatory markers, cytokine levels, and serum samples for future analysis.

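### The only pre-treatment CDAI week sure to exist for every entrant is the one that selected them, so the single-arm CDAI change includes regression to the mean

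*Protocol*

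**What the plan says.** The Study Design line reads "Single center open label interventional pilot study", with 12 participants planned. Change in CDAI over 16 weeks is the first of the Secondary Outcome Measures.

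Inclusion criterion 2 asks for "Crohn's Disease Activity Index (CDAI) > 220 despite at least one conventional therapy", and exclusion criterion 4 bars "Crohn's Disease Activity Index (CDAI) < 220". Under Visit 1 (Screening Visit), patients "complete a Crohn's Disease Activity Index (CDAI) diary for 7 days prior to the baseline visit to determine eligibility". The next sentence adds: "Patient may repeat CDAI diary up to 4 times if the CDAI score does not fall in the qualifying range". This can be read as four diaries in all, or as a first diary plus four repeats.

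Visit 2 (Baseline Visit) lists SIBDQ, blood, ECG, stimulation and device training, but no CDAI. The next CDAI diaries are weekly and kept while the subject stimulates at home: those "During weeks 1-7 to be collected at Visit 3", and those for weeks 8-15, collected at Visit 4. No section names the baseline for the CDAI change.

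**The concern.** A patient's weekly CDAI moves around that patient's own level. Requiring one week to exceed 220 picks weeks that are high partly by chance, and later weeks drift back whether or not the device works. The repeat rule adds to this because it works in one direction: a low week is measured again, a high week is accepted. A first-time qualifier has one pre-treatment week, the selecting one. A repeater has others, but they are the failed ones.

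With no control arm, this fall cannot be separated from an effect of stimulation. A later SAP can choose how to use the data, but it cannot supply an unselected pre-treatment week that was never collected. At stake is a false appearance of clinical improvement in a study whose aim includes efficacy.

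**Working it through.** **Inputs from the protocol.** Cut-off 220; one qualifying 7-day diary; repeats for non-qualifiers only (four or five attempts, depending on reading); follow-up to 16 weeks; one arm; 12 subjects. The protocol states no CDAI mean, SD or bias figure, so there is nothing to reproduce.

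**Assumptions.** A patient's true level is normal with mean *m* and between-patient SD *B*. Weekly error is normal with SD *W*, and errors in adjacent weeks have correlation *r* (first-order autoregressive). The qualifying week is the first score above 220, and stimulation has no effect.

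**One diary, closed form.** With S = √(B² + W²) and a = (220 − m)/S, the expected change is −(W²/S) × φ(a)/(1 − Φ(a)). The error correlation over 16 weeks is negligible: 0.7^16 ≈ 0.003.

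- m/B/W = 220/50/40: S = 64.03, a = 0, so −(1600/64.03) × 0.798 = **−19.9**
- 250/50/40: a = −0.469, so −24.99 × 0.5255 = **−13.1**
- 280/60/30: S = 67.08, a = −0.894, so −13.42 × 0.328 = **−4.4**
- 280/80/40: S = 89.44, a = −0.671, so −17.89 × 0.425 = **−7.6**

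**With repeats, by simulation** (1,000,000 screened per setting). Mean null change from the qualifying week with 1 / 4 / 5 diaries allowed:

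| m/B/W | r = 0 | r = 0.5 | r = 0.7 |
|---|---|---|---|
| 220/50/40 | −20.0 / −26.5 / −27.5 | −19.9 / −22.6 / −23.4 | −19.9 / −20.6 / −21.1 |
| 250/50/40 | −13.1 / −17.7 / −18.5 | −13.1 / −14.6 / −15.0 | −13.1 / −13.1 / −13.3 |
| 280/60/30 | −4.4 / −6.8 / −7.1 | −4.5 / −5.4 / −5.6 | −4.4 / −4.7 / −4.8 |
| 280/80/40 | −7.6 / −11.6 / −12.3 | −7.6 / −9.5 / −9.8 | −7.6 / −8.3 / −8.6 |

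The one-diary figures match the formula within simulation error. With four diaries, the repeats add 20.6 − 19.9 = 0.7 to 26.5 − 20.0 = 6.5 points at mean 220, and 4.7 − 4.4 = 0.3 to 11.6 − 7.6 = 4.0 points at mean 280. The rest is the cut-off.

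**Wider grid.** A separate calculation with independent weekly errors used screened mean 180-280, total SD 60-100, intraclass correlation 0.5-0.8, and four or five attempts. The null fall was about 3 to 54 points from the cut-off alone and 5 to 67 with repeats. The cut-off's share was 62% to 84%.

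**Effect on a test.** The protocol names no test. For a 12-subject paired t-test with a nominal 2.5% chance of falsely showing improvement, that chance becomes about 5-22% with one diary and 5.5-35% with four, over the tabulated settings.

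**After adding a separate week.** In this model the expected error in the week after qualification is *r* times that of the qualifying week, so the remaining bias is *r* times the tabulated value. With four diaries at mean 220 it is 0 at r = 0, 0.5 × 22.6 ≈ 11 at r = 0.5, and 0.7 × 20.6 ≈ 14 at r = 0.7. At mean 280 it is 0, then 3 to 5, then 3 to 6. If the new week also had to exceed 220, −18 to −22 would remain at mean 220.

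**The case against.** Five points can be made on the other side.

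- **The SAP could define the baseline.** The protocol names none, and a SAP might average all screening diaries, including failed ones. At 220/50/40 with four diaries this gives about −13.0 at r = 0.5 and −14.0 at r = 0.7, close to the extra week (−11.4 and −14.4). This stands in part. It depends on failed diaries being kept, it is clearly worse when weeks are independent (−12.5 against 0), and it does nothing for first-time qualifiers. If everyone qualified on the first diary, −20 would remain.
- **The remedy is partial.** At r = 0.7 and mean 220 it removes (20.6 − 14.4)/20.6, about 30% of the bias. This stands and limits what the fix can promise.
- **The mean-220 case is unfavourable.** Half of those screened fail the first diary there, whereas patients with active symptoms and raised calprotectin may score higher. At mean 280 the bias is 4 to 12 points, and at 250/50/40 with r = 0.7 the repeats add nothing. The 35% error rate is the worst corner of the grid. This stands for the size, not for the direction.
- **The problem is generic.** Any single-arm study with a severity cut-off has it, this is a pilot, and CDAI is secondary. That is true and bears on the weight given to the point. It does not explain leaving out an inexpensive unselected week.
- **Calprotectin is not sized.** That is also true, and the point does not rest on it.

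**Conclusion.** The concern holds. The visit schedule guarantees no unselected pre-treatment CDAI week, so the CDAI change is biased towards improvement and no control arm can correct it.

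That the bias favours improvement does not depend on a particular scenario. The cut-off also outweighs the repeats wherever the bias is material. The size in points rests on an assumed mean, SDs and correlation, so confidence in it is medium. This is a change that should be made; it does not invalidate the study.

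The repeat rule does not touch the primary outcome. However, calprotectin has its own entry cut-off of at least 200 μg/g, Visit 2 lists no stool sample, and later stool is planned only for weeks 8 and 16. If the qualifying calprotectin serves as baseline, the same kind of regression can arise there. It is not sized here.

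**What to change.** In the Visit 1 and Visit 2 text, add one 7-day CDAI diary after qualification and before first stimulation. Define it as the baseline for the CDAI change whatever its value, and do not use it for eligibility. Exclusion criterion 4 does not say which diary it refers to, so state that CDAI eligibility is judged on the qualifying diary only. Keep all screening diaries, report how many each subject used, and do not attribute the remaining uncontrolled change to stimulation alone.

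The costs are:

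- One more diary week per subject before Visit 2, and a smaller reported CDAI improvement.
- Some subjects will have a baseline of 220 or less, which must be accepted: with four diaries, 21-38% at mean 220 and 7-17% at mean 280.
- The gap between the qualifying calprotectin and first stimulation grows by a week. Inclusion criterion 3 wants that value "within the past 4 weeks prior to enrollment"; if enrolment means Visit 2, a few values may fall outside the window.

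The CDAI threshold and the planned enrolment of 12 do not change.

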5. After 20 minutes of baseline recording, the gammaCore device will be placed on the left side of the neck in line with the vagus nerve. The nerve lies in the carotid sheath along with the carotid artery and the jugular vein. The carotid pulse is easily felt in the neck. Electrical stimulations are applied using the device for 120 seconds followed by another 120 seconds after a 60 second pause. The amplitude of the stimulation to be used is first calibrated using the lowest possible signal and gradually increasing it to the point where there is mild pulling of the ipsilateral (same side) oral commissure (corner of the mouth where the upper and the lower lip meet). This pulling should not cause any pain to the subject but should be just a slight movement. Once the correct amplitude is reached, the two consecutive stimuli of 120 seconds each will be given to the subject. (The amplitude of the stimulation will be adjusted at each stimulation if necessary to achieve a mild pulling of the ipsilateral oral commissure.) During this time the ECG recordings will continue.
6. After the stimulation period has ended another blood sample (30 mL / 2 tablespoon) to measure insulin levels, and serum for future analysis will be collected approximately 20 minutes post stimulation, and the subject will continue to be monitored and recordings will be made for another 20 minutes. The ECG recordings will be saved as part of the research record.
7. Approximately 40 minutes after the stimulation has ended another blood sample (30 mL / 2 tablespoon) will be collected to measure insulin levels, and stored serum samples for future analysis.
8. The subjects will then be trained on the use of the device using the instructions provided by the manufacturer.
9. The device will be set to the appropriate stimulus and sent with the subject.

The subject will be asked to apply one set of 2 consecutive stimuli, lasting 120 seconds each, 3 times a day till the next visit in 8 weeks.

(Week 1-week 7)

1. Subjects will continue to stimulate the left vagus nerve, one set of two stimulations 120 seconds each, 3 times a day, one in the morning after waking up, one in the afternoon after lunch and one an hour before going to bed.

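### Visits 3 and 4 specify no resting ECG to match the 20-minute baseline for HRV and, if run in the listed order, take cytokine blood after an in-clinic stimulation, unlike baseline

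*Protocol*

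**What the plan says.** The protocol's Secondary Outcome Measures define both cytokines (item 2) and heart rate variability (item 3) as change from baseline over 16 weeks.

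**Visit 2 (baseline).** Cytokine blood is item 2. Item 4 then reads: "A baseline ECG recording using the above placed electrodes will be made for 20 minutes. There is no electrical stimulation taking place currently". Stimulation first occurs at item 5. Afterwards, under item 6, "the subject will continue to be monitored and recordings will be made for another 20 minutes". Blood about 40 minutes after stimulation "will be collected to measure insulin levels, and stored serum samples for future analysis" (item 7). The 20-minute sample in item 6 has the same two uses.

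**Visit 3 (week 8).** Item 1 is "Subject will take one set of two stimulations during the visit to verify compliance and appropriate use of the device". Item 3 is "Blood (29 ml/2 tablespoons) is collected for the inflammatory markers, cytokine levels, and serum samples for future analysis". Item 4 places the ECG electrodes. Item 5 describes two stimulations, the first "followed by another 120 seconds after a 60 second pause. During this time the ECG recordings will continue". Under item 6 the subject stays monitored and "after 20 minutes post stimulation subject will be allowed to go home".

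**Visit 4 (week 16).** The order is the same, but item 5 mentions no pause between the two stimulations.

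**At home.** Between visits subjects stimulate three times a day, "one in the morning after waking up, one in the afternoon after lunch and one an hour before going to bed". Nothing is said about home sessions on the day of a visit.

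**The concern.** A change from baseline is interpretable when both measurements are made under the same conditions. Here baseline blood and the baseline resting ECG come from people who have had no study stimulation. At follow-up, a stimulation set heads the list of procedures, and no resting ECG period is described.

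If stimulation has a short-lived effect on cytokines or on heart rate variability, the measured change combines that acute effect with any lasting effect of 8 or 16 weeks of treatment. With a single arm there is no control group to separate the two. The protocol itself treats within-visit effects as worth looking for: it draws insulin about 20 and 40 minutes after the first stimulation and records ECG through and after it. Its background also reports that non-invasive stimulation lowers TNF-alpha in healthy people, though without saying how quickly or by how much.

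This is a matter for the protocol. An analysis plan cannot recover a resting ECG that was never recorded, or change when blood was drawn.

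**Working it through.** The protocol gives no figure to reproduce on this point. The main check is a comparison of the three visits.

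| Step | Visit 2 | Visit 3 | Visit 4 |
|---|---|---|---|
| Stimulation listed before blood | none | item 1 | item 1 |
| Cytokine blood | item 2 | item 3 | item 3 |
| ECG electrodes | item 3 | item 4 | item 4 |
| Stated stimulation-free ECG before stimulation | 20 min (item 4) | none | none |
| Described stimulation, ECG continuing | item 5 | item 5 | item 5 |
| Length of that period | 120 + 60 + 120 = 300 s = 5 min | 300 s = 5 min | 120 + 120 = 240 s = 4 min as written |
| After stimulation | ECG recording stated, at least 20 min | monitored 20 min, ECG recording not stated | as Visit 3 |

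**Reading A: items 1 and 5 are two sets, run as listed.** Blood and ECG at weeks 8 and 16 follow an in-clinic stimulation. At baseline both precede any stimulation. Cytokines and HRV are both mismatched.

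**Reading B: item 1 announces the set delivered at item 5.** Blood then precedes the in-clinic stimulation, as at baseline, and the in-clinic cytokine problem disappears. The HRV gap remains, because no timed or resting recording lies between electrode placement and stimulation. The word *continue* in item 5 implies that recording starts earlier, but gives neither a length nor a rest condition.

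**Both readings.** Stated resting ECG is 20, 0 and 0 minutes at Visits 2, 3 and 4. Zero means none stated; it does not show that none would be taken. The only ECG segment stated at all three visits is the one under stimulation. A home set after waking may also precede the clinic measurements.

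**Illustration of size.** The protocol names no test and gives no acute effect, so the shifts below are assumptions. Suppose there is no lasting effect and a two-sided 5% paired t-test is used. Let d be the acute shift in SDs of the paired difference. The test statistic is noncentral t with n − 1 degrees of freedom and noncentrality d√n; for example, 0.5 × √12 = 1.73 with 11 degrees of freedom. The probability of declaring a change is:

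| d | 12 completers | 10 completers |
|---|---|---|
| 0.1 | 0.062 | 0.059 |
| 0.2 | 0.097 | 0.088 |
| 0.3 | 0.158 | 0.136 |
| 0.5 | 0.353 | 0.293 |
| 0.8 | 0.714 | 0.616 |
| 1.0 | 0.883 | 0.803 |

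A shift of 0.1 SD barely moves the nominal 5%. Shifts of half an SD or more would often be read as a treatment change.

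**The case against.** The more natural reading may be the benign one. Item 1 states a purpose, says only that the set is taken at some point in the visit, and item 6 refers to a single stimulation period. On that reading blood precedes the in-clinic stimulation at every visit. This has force: the cytokine part is an ambiguity and not a demonstrated mismatch. But item 1 is numbered first, nothing excludes two sets, and staff could run the visits differently from one participant to the next.

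On HRV, recording evidently starts before item 5, the protocol never says the outcome is resting HRV, and the choice of ECG segment may be left to an analysis plan. That is fair as to definition. The length and condition of the recording to be collected are nonetheless protocol matters, and the protocol's own baseline sets a 20-minute stimulation-free standard that follow-up does not repeat.

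There are partial substitutes. HRV could be compared under stimulation at all visits, or after stimulation if the monitoring at Visits 3 and 4 were clarified to include ECG recording. Neither measures resting vagal tone. Serum banked after stimulation at Visit 2 could help gauge an acute cytokine shift, but no cytokine assay of it is stated.

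Finally, subjects on treatment three times a day will always have stimulated recently, so follow-up can never fully match an untreated baseline. That stands. It limits what reordering can achieve, and is the reason to record the last home session.

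**Conclusion.** The concern holds. On either reading the protocol specifies no follow-up ECG that matches the 20-minute resting baseline, so the HRV change has no secured like-for-like resting comparison. For cytokines the mismatch depends on items 1 and 5 being separate sets run in the listed order, which the text leaves open.

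Two of four secondary outcomes are affected. Fecal calprotectin, CDAI and insulin are not. The documents give no size or time course for an acute effect. The TNF-alpha statement in the background is not tied to a time after stimulation, so it does not establish an acute direction either. The error rates above therefore show sensitivity to assumed shifts and are not an estimate of bias in this trial. The change is worth making because the mismatch is avoidable at low cost and cannot be repaired afterwards.

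**What to change.** 1. At Visits 3 and 4, place the cytokine blood draw and a 20-minute stimulation-free ECG matching Visit 2 before any in-clinic stimulation.
2. Define the cytokine and HRV outcomes on these measurements, taken before in-clinic stimulation, at baseline, week 8 and week 16.
3. Record the time of the last home session before each of these visits and report it with the results. Reordering the clinic steps does not remove the effect of a home set on the same day.
4. Reconcile whether items 1 and 5 are one set or two, and reconcile item 5 between Visit 3 (60-second pause) and Visit 4 (no pause stated).

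**Cost.** About 20 more minutes of ECG, and so a longer stay, at each of two visits: 2 × 20 = 40 minutes per participant, and 40 × 12 = 480 minutes = 8 hours over the study. One data field is added. No new procedure is needed.

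### At Visits 3 and 4 a device set is listed before the cytokine blood draw, while the Visit 2 draw precedes any stimulation, so the cytokine change from baseline may include a short-term post-stimulation effect

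*Protocol*

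**What the plan says.** Secondary outcome 2 is the change in serum cytokines, including C-reactive protein, over 16 weeks. The Protocol defines the comparison in one sentence: "Cytokine levels within the blood will be assessed and compared to baseline levels".

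At Visit 2 (Baseline Visit), item 2 reads: "Blood (30 ml/2 tablespoons) is collected under aseptic conditions for the inflammatory markers, cytokine levels, insulin levels, and serum samples for future analysis". Item 4 is a 20-minute ECG recording, of which the Protocol says: "There is no electrical stimulation taking place currently". Item 5 is the first device use: "After 20 minutes of baseline recording, the gammaCore device will be placed on the left side of the neck in line with the vagus nerve".

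At Visits 3 and 4, item 1 reads: "Subject will take one set of two stimulations during the visit to verify compliance and appropriate use of the device". Item 2 is the SIBDQ. Item 3 is the cytokine draw: "Blood (29 ml/2 tablespoons) is collected for the inflammatory markers, cytokine levels, and serum samples for future analysis". Item 4 is electrode placement, and item 5 begins: "The gammacore device will be placed on the left side of the neck in line with the vagus nerve". No interval between stimulation and blood draw is stated at these visits, and nothing links item 1 to item 5.

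Between visits, subjects use the device three times a day, including after waking. The Protocol gives no instruction about the home set on the day of a visit.

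**The concern.** A change from baseline is interpretable when both samples are taken under the same conditions apart from the treatment exposure of interest. Here the baseline sample comes from a subject who has never been stimulated in the study. Read in its listed order, each follow-up sample comes from a subject who finished a device set with only a short questionnaire in between.

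The Protocol's background gives some reason to care about this: "In healthy humans nVNS has been shown to decrease tumor necrosis factor" (the sentence concerns TNF-alpha levels). If stimulation moves cytokines briefly, a fall present only in the period after a set would be reported as a change at weeks 8 and 16, even if levels away from stimulation had not moved. With one open-label arm, no comparison group shares the sampling schedule and could absorb the effect. No draw at Visits 3 or 4 is specified as preceding in-visit stimulation.

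**Working it through.** The Protocol states no figure on this point, so there is none to reproduce. The check is of the order of steps, followed by a count and an illustration of scale.

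**1. Order of steps**

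| Step | Visit 2 | Visits 3 and 4 |
|---|---|---|
| Witnessed set of two stimulations | none | item 1 |
| SIBDQ | item 1 | item 2 |
| Cytokine blood | item 2 | item 3 |
| ECG electrodes | item 3 | item 4 |
| 20-minute recording without stimulation | item 4 | not listed |
| Stimulation under ECG | item 5 | item 5 |

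The baseline draw is free of stimulation on any reading. The follow-up draw has stimulation listed on both sides of it.

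**2. Count of samples affected**

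Input: 12 planned participants (Estimated Enrollment), two follow-up visits, no withdrawals assumed.

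- Follow-up samples: 12 × 2 = 24. Baseline samples: 12.
- If the items are done in the listed order, 24 of 24 follow-up samples and 0 of 12 baseline samples come after an in-visit set.
- If items 1 and 5 describe one set, done at the item 5 position, 0 of 24 follow-up samples do.
- If practice differs between subjects or visits, the count lies between 0 and 24 and the interval varies.

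**3. Scale, for illustration only**

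The Protocol gives no effect size, standard deviation, test or alpha for cytokines. Assume a two-sided 5% paired t-test with n = 12, no longer-term change at all, and a short-term shift at the follow-up draw of d standard deviations of the within-subject change. The test statistic then follows a noncentral t distribution with 11 degrees of freedom and noncentrality d × √12. The critical value is 2.201.

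| d (assumed) | d × √12 | Probability of a significant result |
|---|---|---|
| 0.1 | 0.35 | 6.2% |
| 0.25 | 0.87 | 12.4% |
| 0.5 | 1.73 | 35.3% |
| 0.75 | 2.60 | 65.8% |
| 1.0 | 3.46 | 88.3% |

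The nominal rate is 5%. The result runs from almost no distortion to a finding driven mostly by sampling time, and nothing in the documents says where d lies.

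**4. What the stored serum could recover**

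Serum is kept at about 20 and 40 minutes after the first stimulation at Visit 2. Assayed against the draw before stimulation, it could estimate the short-term effect of a first set. It cannot give the level without recent stimulation at week 8 or week 16, or the short-term effect after weeks of use three times a day.

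**The case against.** The strongest reply is that items 1 and 5 are one set. Item 1 is timed only as happening at some point in the visit and gives a purpose, checking compliance and technique. Item 5 gives the execution. Items 2 to 5 at the follow-up visits otherwise track the Visit 2 order, and item 6 refers to a single stimulation period. No text makes the item numbers a binding sequence. On this reading blood precedes in-visit stimulation at every visit. The reading is plausible, and it is why the count is an upper limit. It does not close the point: the lists otherwise run in time order, item 1 comes first, and a coordinator could reasonably do it first.

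A reader might infer that the sponsor's own rationale predicts an acute cytokine fall, so that the 16-week change is certainly contaminated. The documents do not support this. The background sentence on TNF-alpha gives no time course, number of sessions or size. Insulin is the only named measure assigned to sampling minutes after stimulation.

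A reader might also infer that the endpoint is meant to capture a sustained effect free of recent stimulation. The Protocol does not say so; it speaks only of comparison with baseline. Levels during regular use are a legitimate target. That target still needs a defined interval since the last set, and the Protocol fixes none.

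Finally, this is one secondary outcome of a 12-person pilot. That stands. The primary outcome comes from stool that may be collected within a week of the visit, and its value does not depend on the order of steps inside the visit.

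**Conclusion.** The point holds as a possible bias in secondary outcome 2. The documents establish three things: the Visit 2 cytokine draw precedes any stimulation; a device set is listed before the draw at Visits 3 and 4; and the relation of items 1 and 5, and the interval from stimulation to draw, are left open. Followed as listed, the mismatch affects up to 24 of 24 follow-up samples against 0 of 12 at baseline.

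Whether this distorts the result depends on a short-term effect on cytokines, which the documents neither show nor exclude. The right wording is that the change from baseline may mix the two effects. The probabilities in the illustration rest on an assumed test, alpha and shift, and are not estimates for this trial. The change is worth making because the mismatch is avoidable at almost no cost, and because a sample drawn after stimulation cannot later be turned into one drawn before it.

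**What to change.** In the Visit 3 and Visit 4 lists:

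1. Reconcile items 1 and 5 by stating whether they are one set or two.
2. Place the cytokine draw before any in-visit stimulation, as at Visit 2, and state that this order is required.
3. Record the clock time of the last home set before each follow-up draw, together with the time of the draw.

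The cost is a re-ordered visit list in an amendment and one extra form field for the home set, with no new sample, procedure or visit. The limit is that a home set after waking may still precede the draw. The interval then becomes known and can be reported with the result, but the never-stimulated condition of the baseline sample is not fully restored.
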